#### **Preliminary work:**

##### ***Acute human LFP recording:***

We have performed acute prefrontal cortical LFP recordings in over 30 patients with Parkinson's disease and patients with epilepsy undergoing brain surgery, under an IRB approved protocol funded by The Defense Advanced Research Projects Agency (DARPA). For this study, in addition to the DBS lead implanted in the basal ganglia, a cortical electrode is temporarily placed over the PFC. Brain signals are then recorded for a short period of time while patients are resting or engaged in tasks. Cortical stimulation is then used to modulate non-motor symptoms such as anxiety and depression. We found that stimulation of the PFC induced positive affect in these patients. Although promising, these results are limited by the temporal and logistical constraints of human intraoperative studies, and chronic brain signals recordings are required to overcome these limitations and better understand and treat these symptoms. This will be achieved using Activa PC+S and Summit RC+S, the two devices allowing both long-term recording of brain activity and therapeutic treatment of the motor-symptoms.

### **Activa PC+S studies in animal models.**

Several animal studies, including one from our group (13), have shown successful implantation of the Activa PC+S device. These animal data supported initiation of trials in human patient populations by showing:

- 1) Safety and maintenance of good health and motor function of the animals,
- 2) No underlying cortical damage as shown by a lack of cellular astrocytic and immuno-reactivity,
- 3) Lack of lead migration (based on stability of recording of characteristic M1 physiology),
- 4) Chronic stable recordings from the cortex using a subdural electrode connected to Activa PC+S may be maintained for 2 years

[figure not shown]

**Figure 3:** Movement-related changes in ECoG activity detected using Activa PC+S 6 months after implantation. Activity is observed in electrodes covering the primary motor cortex (right panel). A time-frequency plot (left panel) is aligned on movement onset (vertical line,). Movement onset is associated with a typical power decrease in the beta band (13-30Hz) and power increase in the gamma band (50-250Hz).

### Other human studies using bidirectional neural interfaces

Several on-going human clinical trials currently implement the Activa PC+S for treatment-resistant depression (15), movement disorders (16) and Tourette's syndrome (17). Additional studies using a different closed-loop brain stimulation system (RNS, Neuropace Inc.) have been conducted in patients with epilepsy (18) and Tourette's syndrome (19). Currently, three similar and active research protocols using Summit RC+S have obtained FDA (G180097; G180203; G160018-S001) and IRB approval.

## 2.0 Clinical Study Outline

This study will use the Activa PC+S device in PD patients scheduled to undergo DBS implantation for the treatment of motor fluctuations, who also have concurrent non-motor symptoms. The PC+S will be attached to permanent ipsilateral prefrontal cortex and basal ganglia electrodes, to record cortical and subcortical brain signals during different mood/behavioural states (for example: anxious vs calm, depressed vs happy, impulsive vs thoughtful). The study design will allow us to identify abnormal neural activity corresponding

with non-motor symptoms associated with PD and investigate how stimulation can alleviate these symptoms. We plan to offer the Summit RC+S device or a standard Medtronic pulse generator to patients who have already been enrolled in the trial if their Activa PC+S devices are nearing end of battery life. The Summit System has not been evaluated for MR compatibility (like the PC+S). It also requires frequent recharge and stimulation programming for this device is restricted to the use of a special clinician programmer with limited distribution. These considerations will be discussed with patients before signing the consent form. Patients who do not qualify or decline the replacement of PC+S with the RC+S will be implanted with the commercially available DBS device compatible with their brain electrodes.

## **2.1 Study Objectives**

This study will allow us to both define the neural correlates of non-motor symptoms as well as to test the efficacy of stimulation in alleviating these symptoms. The Medtronic Activa PC+S device will allow us to monitor cortical and subcortical brain signals while non-motor symptoms of PD are assessed by subjective (i.e. patient reports and questionnaires) and objective measures (blood pressure, electrodermal activity, and/or task performance in tasks that probe emotional state). Using Nexus-D and E, we will then develop closed-loop paradigm using the physiological biomarker underlying non-motor symptoms, identified in the first phase of this study, to automatically adjust stimulation parameters. Finally, using Nexus-D we will train patients to voluntarily modulate their abnormal brain signals to reduce symptoms. Summit RC+S will allow us to implement the fully closed-loop deep brain stimulation paradigm and neurofeedback components.

## **3.0 Investigational Plan**

This is a single-center study of the neurophysiology of non-motor symptoms associated with Parkinson's disease with several goals: (1) define the electrophysiological correlates (potential biomarkers) of non-motor symptoms (i.e. abnormal oscillatory activity), (2) determine the stimulation parameters that can disrupt such abnormal oscillatory activity and reduce these symptoms, (3) integrate potential electrophysiological biomarker into a closed-loop DBS paradigm and into neurofeedback training.

In a cohort of 10 subjects, we will assess the feasibility of improving non-motor symptoms using closed-loop stimulation. Upon UCSF Institutional Review Board (IRB) approval of our investigational plan and protocol, we propose to conduct this study in two phases for each subject. In phase 1 (1-7 months), patients will undergo long-term recordings of brain signals from electrodes placed over the PFC and in the basal ganglia (subthalamic nucleus or globus pallidus) along with monitoring of the severity of their non-motor symptoms. Since non-motor symptoms may fluctuate spontaneously and in response to dopaminergic treatment or basal ganglia stimulation, neural data will be recorded at multiple time points, in medication on and off states as well as in stimulation on and off states. At each brain data recording session non-motor symptoms will be assessed. Brain signals and symptom assessments will then be analyzed in order to identify a neuronal correlate, a biomarker, of non-motor symptoms and determine how stimulation modulates this abnormal brain activity. In the latter part of phase I, the effects of acute and chronic open loop cortical stimulation will be assessed.

In phase 2 (8 months - 5 years), we will develop a closed-loop paradigm that will automatically determine stimulation settings that optimally reduce non-motor symptoms based on the biomarker identified in phase 1. Using that biomarker we will also train patients to voluntarily modulate these abnormal signals. Subjects will be asked to voluntarily minimize the aberrant signals as represented by the position of a cursor on a screen, while their non-motor symptoms are assessed

In both phases, data will be collected in clinic and/or at the patient's home. Non-motor symptom assessments will include both long-term and short-term time scales. Validated patient self-report questionnaires widely used by psychiatrists and neuropsychologists will be used to assess chronic symptoms over a 2 to 4 week time period. The Beck depression inventory-2nd edition (BDI-II), the Beck anxiety inventory (BAI), Hospital Anxiety and Depression Scale (HADS), Apathy Evaluation Scale (AES), Questionnaire for Impulsive-Compulsive Disorders in Parkinson's disease (QUIP), Yale-Brown Obsessive Compulsive Scale (YBOCS), and other well-validated questionnaires will be used. In addition, acute symptoms at the time of the recordings will be assessed using visual analogue scales and tasks engaging emotional and decision making processes, in which performance parameters such as accuracy and reaction time may correlate with non-motor symptoms.

#### **4.0 Patient Eligibility**

##### Inclusion criteria:

- 1.) Ability to give informed consent for the study
- 2.) Age 30-75
- 3.) Diagnosis of Parkinson's disease by a movement disorders specialist
- 4.) Movement disorder symptoms that are sufficiently severe, in the setting of best medical therapy, to warrant surgical implantation of deep brain stimulators according to standard clinical criteria
- 5.) UPDRS-III score off medication between 20 and 80 and an improvement of at least 30% in the baseline UPDRS-III on medication score, compared to the baseline off-medication score.

OR

Patients with tremor-dominant PD (a tremor score of at least 2 on a UPDRS-III sub-score for tremor), treatment resistant, with significant functional disability despite maximal medical management

OR

Patients intolerant to medication causing significant functional disability

- 6.) Have one or several mild to moderate mood or impulsive behavior as defined by:
  - depression (BDI>=13)
  - anxiety (BAI >=7)
  - impulsive behavior as indicated by a positive score on the QUIP-A (Questionnaire for Impulsive-Compulsive disorders in Parkinson's Disease) or as determined by clinical interview or informant report
  - Mood or behavior symptom fluctuations corresponding to minimum 30% improvement in non-motor symptoms when comparing visual analogue scales (VAS) scores in the on versus off medication state

- 7.) Stable doses of anti-Parkinsonian medications for at least 30 days prior to their baseline assessment.
- 8.) Patients considered for the replacement of the PC+S with the summit RC+S device would meet the following criteria:
  - a. Ongoing clinical need as determined by clinical team. This would be defined as still having depression / anxiety causing significant discomfort.
  - b. Cognitive capacity to take part in symptoms assessments associated with closed loop cortical stimulation.
  - c. Clinical evidence of benefit from acute cortical stimulation.
  - d. Cortical biomarker associated with depression and anxiety and identified in the early phase of this study.
  - e. Evidence of benefit of closed loop cortical stimulation (as determined by quantitative visual analogue subjective self-reports).
  - f. Ability to recharge the system (either patients and/or caregivers').
  - g. Ability to receive re-programming care at UCSF or an institution with access to the clinician programmer that is specific to the investigational Medtronic Summit RC+S device and with limited distribution.
- 9.) Patient receiving the replacement under this protocol must be within the 5 year study duration that this protocol covers.
  - a. The replacement will be provided so that the remaining time in the 5 year protocol can be completed.

Exclusion criteria:

- 1.) Pregnancy or breast feeding
- 2.) MRI showing cortical atrophy out of proportion to age
- 3.) MRI showing focal brain lesions that could indicate a disorder other than idiopathic PD
- 4.) Major comorbidity increasing the risk of surgery (prior stroke, severe hypertension, severe diabetes, or need for chronic anticoagulation other than aspirin)
- 5.) Any prior intracranial surgery except DBS surgery
- 6.) Significant cognitive impairment (MoCA<20).
- 7.) History of seizures
- 8.) Immunocompromised
- 9.) Has an active infection
- 10.) Requires diathermy, electroconvulsive therapy (ECT) or transcranial magnetic stimulation (TMS) to treat a chronic condition
- 11.) Inability to comply with study follow-up visits
- 12.) Active suicidal based on Suicide Severity Rating Scale (SSRS) and no previous attempts
- 13.) Any personality or mood symptoms that study personnel believe will interfere with study requirements.
- 14.) For battery replacement, previous deep brain stimulation surgery using an RC+S incompatible system.

We are not setting a minimum on-medication UPDRS score, because in patients with severe motor fluctuation the on-medication score may be quite low. Such patients can be excellent surgical candidates because the major benefit of therapy is experienced in an effectively “off medication” state, which is of real benefit in patients who fluctuate between “on” and off” states in spite of frequent medication dosing.

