Efficacy Assessments	Non-motor symptoms will be assessed by validated questionnaires: BDI= Beck Depression Inventory, BAI= Beck Anxiety Inventory, HADS= Hospital Anxiety and Depression Scale, QUIP= Questionnaire for Impulsive-Compulsive Disorders in Parkinson's Disease, YBOCS= Yale-Brown Obsessive Compulsive Scale. Since these scales assess symptoms over the previous few weeks period, visual analogue scales (VAS) will be used to assess the non-motor symptoms at the time of the recordings. In addition, objective measure such as blood pressure, electrodermal activity, electromyography and/or task performance such as reaction time and error rate might also be used to assess non-motor symptoms.
Safety Assessments	
1) Physical examination at all study visits
 
2) Baseline evaluation and regular clinical follow up with the study psychiatrist
 
3) Check of pulse generator stimulation parameters, impedance measurements, and battery voltage at all study visits
 
4) Surgical or nonsurgical adverse events as recorded on case report forms
 
5) Assessment of suicidality using the Columbia Suicide Severity Rating Scale, at protocol-defined outpatient visits
 
6) In visits where the Nexus D and/or E system will be used for closed loop stimulation, all possible stimulation settings are preselected by clinicians to avoid the possibility of producing major stimulation-induced adverse effects
 
7) When closed loop stimulation is used out of the clinic, patients can exit closed loop mode at any time, using a hand-held controller, and return to their normal clinical settings

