## 6.0 Study Procedure

*Study Duration:* The duration of this pilot study will be 5 years. We expect that all 10 patients will be recruited in the first 3 years, and data collection will be completed at 8 years.

*Patient recruitment:* PD patients will be recruited from the UCSF Surgical Movement Disorders Clinic. From this clinic population, 50 PD patients/year are typically offered DBS. Prior to the start of the study, an informal phone interview to schedule an in-clinic evaluation will take place, followed by the pre-surgical in-clinic evaluation. This baseline visit will be scheduled to: 1) confirm eligibility, 2) acquire patient demographics, 3) review medical history and report vital signs, 4) ensure patients are not currently pregnant or plan to become pregnant, 5) obtain a list of current medications being taken, 6) ensure MoCA score meets inclusion criteria ( $\geq 20$ ), 7) obtain a baseline clinical characterization of motor symptoms using the UPDRS III both on and off medication, 8) obtain a baseline clinical characterization of motor and non-motor symptoms on and off medication, 9) obtain an anatomical MRI for future surgical planning and to further determine eligibility under inclusion/exclusion criteria.

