*Clinical characterization:* Study visits are summarized in **Table 2**. Motor and neuropsychological characterization will be performed by a movement disorders neurologist, neuropsychologist and psychiatrist at baseline (preoperative visit), at the one year and two years follow up visits. Motor symptoms will be assessed using the Unified Parkinson's Disease Rating Scale (UPDRS) parts I-V and the dyskinesia rating scale (UDysR), on medication. The UPDRS part III will be performed both on and off medication (12 hours). At the one and two year visit, all patients will be assessed using the Clinician Global Impression of Change (CGI-C) and Patient Global Impression of Change (PGI-C) to adequately assess effectiveness that may not be captured by motor rating scales. Neuropsychological evaluation will include the following test battery: Montreal Cognitive Assessment (MoCA), the Columbia Suicide Severity Rating Scale (C-SSRS), Symbol-Digit Modality Test (SDMT, written and oral versions); Delis Kaplan Executive Function System (DKEFS Trail making test, Design Fluency), Neuropsychological Assessment Battery (NAB Digit Span, Memory, Visual Discrimination); Rey-Osterreith Complex Figure (ROCF Copy & Immediate Trials); Controlled Oral Word Association (COWA, FAS & Animal Fluency), Boston Naming Test; Beck Depression Inventory-2nd Edition (BDI-II); Beck Anxiety Inventory (BAI); Parkinson's anxiety scale (PAS); Hospital Anxiety and Depression scale (HADS); Apathy Evaluation Scale (AES), Questionnaire for Impulsive-Compulsive Disorders in Parkinson's Disease (QUIP), Yale-Brown Obsessive Compulsive Scale (YBOCS), and Visual Analogue Scales (VAS). Several of these tests (MoCA and Neuropsychological Assessment Battery) have alternative forms available, which will be used to avoid practice effects.

On all other study visits, clinical characterization will be performed by trained study personnel and will include non-motor symptoms evaluation using a subset of the scales listed above, depending on the patient's predominant non-motor symptoms. In addition the patient will perform tasks engaging emotion and/or decision processes. Rating scale examinations and task performance will be videotaped.

On all outpatient study visits we will also administer the Columbia Suicide Severity Scale (C-SSRS).

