**Table 2. Summary of study visits**

Study Visit	Time	Purpose	Therapeutic Conditions	Behavioral Conditions
Pre-surgery	Within 90 days prior to surgery	Clinical: Evaluation of motor and neuropsychiatric symptoms	Stimulation: NA  Medication: off then on	-Behavioral tasks  -Symptom evaluation
		Research: Informed consent; ensure eligibility; Patient will perform computer-based tasks that engaged emotion and cognition		
1 (START OF PHASE I)	Day of surgery	Clinical: DBS Implantation and CT scan	Stimulation: DBS off  Medication: surgical anesthesia	-Rest  -Symptom evaluation
		Research: Record brain signal during surgery; evaluate the severity of anxiety and depression; verification of electrodes placement		
2	1 day after implantation, prior to hospital discharge	Clinical: postoperative follow up	Stimulation: DBS off  Medication: off and on	-Rest and behavioral tasks  -Symptom evaluation
		Research: Record brain signals with and without dopaminergic medication in order to study the effect of antiparkinsonian medication on brain signals and patient's symptoms		
3	10 days after implantation (+/- 5 days)	Clinical: Staple removal and wound check	Stimulation: DBS off  Medication: off and on	-Rest and behavioral tasks  -Symptom evaluation
		Research: Record brain signals with and without dopaminergic medication in order to		

		study the effect of antiparkinsonian medication on brain signals and patient's symptoms		
4	3 weeks after implantation (+/- 10 days)	Research: Record brain signals with and without dopaminergic medication in order to study the effect of antiparkinsonian medication on brain signals and patient's symptoms	Stimulation: DBS off Medication: off and on	-Rest and behavioral tasks -Symptom evaluation
5	4 weeks after implantation (+/- 10 days)	Clinical: DBS initial programming  Research: Record brain signals with and without dopaminergic medication in order to study the effect of antiparkinsonian medication on brain signals and patient's symptoms	Stimulation: DBS off Medication: off and on	-Rest and behavioral tasks -Symptom evaluation

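### Exclusion criterion 12 is worded so that an actively suicidal patient with a previous attempt is not excluded, and the intended rule on previous attempts is unclear

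*Combined protocol and SAP*

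**What the plan says.** Section 4.0, Patient Eligibility, has fourteen numbered exclusion criteria. Number 12 reads: "Active suicidal based on Suicide Severity Rating Scale (SSRS) and no previous attempts". It is the only explicit suicide-risk criterion in the supplied text.

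Two places tell staff when to apply the criteria. Section 6.0, under patient recruitment, says: "This baseline visit will be scheduled to: 1) confirm eligibility", and goes on to eight further tasks. Table 2, in the pre-surgery row, gives the research purpose as: "Informed consent; ensure eligibility; Patient will perform computer-based tasks that engaged emotion and cognition". Both point back to Section 4.0, and neither rewords item 12.

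Other provisions bear on suicide risk without setting an eligibility rule for it:

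- The Synopsis lists among the safety assessments: "Baseline evaluation and regular clinical follow up with the study psychiatrist".
- Section 6.0, under clinical characterization, has a psychiatrist take part at baseline and puts the Columbia Suicide Severity Rating Scale (C-SSRS) in the baseline battery. It gives no C-SSRS result that decides eligibility.
- Inclusion criterion 6 opens: "Have one or several mild to moderate mood or impulsive behavior as defined by".
- Exclusion criterion 13 lets study personnel exclude a patient whose mood or personality symptoms they expect to interfere with what the study requires.

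**The concern.** The two halves of item 12 point in opposite directions. Active suicidality is a reason to keep a patient out. Having no previous attempts is the kind of condition one would ask of a patient being let in. Joined by *and* in an exclusion list, the second half narrows the first: a previous attempt takes the patient outside the exclusion.

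This matters because the trial deliberately selects patients with depression, anxiety or impulsivity, and staff must settle eligibility before a permanent subdural prefrontal lead is added to the planned DBS surgery. A safety criterion that gives the wrong answer when followed to the letter is more than a stylistic fault.

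A second, more everyday problem is the patient who has a previous attempt but is not currently suicidal. The text does not show whether the sponsor meant to exclude that patient, and two careful assessors could decide differently.

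**Working it through.** There is no figure in the plan to reproduce. The check is a truth table, followed by a search for other text that would settle the rule.

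**Step 1. The rules compared.** Let A be actively suicidal on the scale and P be at least one previous attempt.

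- Literal text: exclude if A and not P.
- Possible intention 1, only active suicidality excludes: exclude if A.
- Possible intention 2, a previous attempt also excludes: exclude if A or P.

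The two intentions are candidates for what the sponsor may have meant, not recommendations.

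**Step 2. Apply each rule to the four profiles.**

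| Profile | Literal text | Intention 1 | Intention 2 |
|---|---|---|---|
| Active, previous attempt | not excluded | excluded | excluded |
| Active, no previous attempt | excluded | excluded | excluded |
| Not active, previous attempt | not excluded | not excluded | excluded |
| Not active, no previous attempt | not excluded | not excluded | not excluded |
| Profiles excluded | 1 of 4 | 2 of 4 | 3 of 4 |

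The literal text differs from intention 1 in 2 − 1 = 1 profile (active, previous attempt). It differs from intention 2 in 3 − 1 = 2 profiles (that one, and not active with a previous attempt). The first row is wrong under both, so the fault does not depend on which intention is right. The literal text would be correct only if a previous attempt was meant to make an actively suicidal patient eligible, and nothing in the documents supports that.

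**Step 3. Look for text that corrects or overrides item 12.**

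- The nine baseline tasks in Section 6.0 name checks on pregnancy (task 4), cognition (task 6) and MRI (task 9). None states a suicidality rule.
- Table 2 adds only the general instruction on eligibility.
- The C-SSRS and the psychiatrist's evaluation produce information, but no text says how the result decides entry.
- Inclusion criterion 6 sets a ceiling in words only; its scale cut-offs are lower bounds (BDI of at least 13, BAI of at least 7). It does not mention suicidality.
- Exclusion criterion 13 is discretionary, and its test is interference with study requirements rather than suicide risk.

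Nothing in the supplied text repairs item 12. The Case Report Form and Risk Assessment (Appendices C and D) are not in the supplied text, so nothing is claimed about them.

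**The case against.** The strongest reply is that nobody would apply the item literally. A psychiatrist sees the patient at baseline, the C-SSRS is given, Table 2 includes a clinical evaluation of neuropsychiatric symptoms before surgery, inclusion criterion 6 limits severity in words, and exclusion criterion 13 gives staff a way to decline. For harm to follow, someone would have to treat a previous attempt as a reason to admit an actively suicidal patient. That is unlikely, and this part of the objection stands. It bears on how probable harm is, not on whether the wording is right.

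A second reply is that the intention is less doubtful than it looks. If only active suicidality mattered, the words on previous attempts would do no work, so the likelier meaning is that both conditions were to be absent. The protocol mixes inclusion and exclusion phrasing elsewhere: a MoCA below 20 is an exclusion criterion, yet Section 6.0 has staff "ensure MoCA score meets inclusion criteria". This is fair evidence for intention 2, but it is an inference. A reader deciding on a patient with a past attempt and no current suicidality still has no stated rule.

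Two further points are accepted. The profile counts are unweighted and measure the rule, not a risk. And the silence of the baseline task list is weak evidence by itself, because its named checks cover only exclusion criteria 1, 2, 3 and 6; most of the other criteria are not restated there either. It shows only that the list does not rescue item 12.

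**Conclusion.** The concern holds. As written, exclusion criterion 12 excludes one of four profiles and misses the actively suicidal patient with a previous attempt under either plausible intention. The handling of a patient with a previous attempt who is not currently suicidal is not settled by the supplied text.

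Confidence is high for the wording only. It rests on reading the item as part of an exclusion list with its two conditions joined by *and*, and on the supplied text without the appendices. No effect on enrolment or harm can be quantified, because the documents give no frequency of active suicidality or of previous attempts, and the safeguards make enrolment through the gap unlikely. Sample size and planned analyses are untouched. It should be fixed because it is a clear error in a safety criterion and is easy to correct.

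**What to change.** Split item 12 into two separate statements, one on active suicidality and one on previous attempts, so that a previous attempt no longer cancels the exclusion for active suicidality. In the second statement the sponsor should make its own intended rule explicit; which rule applies is the sponsor's decision and is not proposed here. As an optional clarification, separate from the error, the item could name the rating-scale result that counts as actively suicidal.

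The cost is a short wording amendment, which Section 10.0 requires to go to the IRB before it is implemented. Sample size, visits and analyses do not change.
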